# Appendix A. Time and Events Schedule

a The screening visit should occur within 3 months before study agent administration.

b The baseline (BL) visit should occur within 7 days before study agent administration.

c Long-term follow-up (LTFU) evaluations once a year for years 2-5.

d An early termination (ET) visit will be sought for any subject who withdraws from the study before the Year 1 visit. Perform the evaluations indicated as  $\checkmark^*$  if the ET visit occurs before the last visit at which these tests are required.

e DNA testing for participants who have not had a mutation in the RS1 gene documented previously.

f Physical exam, safety labs and coagulation may be obtained at either the screening or baseline exam.

g Safety labs include hematology and clinical chemistry as specified in Section 6.4.

h Clinical evaluation consists of an interim medical history, including use of carbonic anhydrase inhibitors and other medications, review of AEs, and a symptom-directed physical examination.

i Ophthalmic examinations include slit lamp examination, tonometry, indirect ophthalmoscopy and retinal biomicroscopy in both eyes will be evaluated at each visit, except on Day 0 (Visit 3) when the only required exam is tonometry of the study eye about 30 minutes after study agent administration is completed.

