Subjects who prematurely discontinue from the study after administration of rAAV2tYF-CBhRS1 will not be replaced, unless they are lost to follow-up before a DSMC review at which the safety data from their Week 2 visit is required for a decision to progress to the next dose treatment group. All subjects who prematurely discontinue from the study after administration of the study agent will be encouraged to complete an early termination (ET) visit.

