# 6.15 Long-term Follow-up

After the completion of 9 study visits over the course of one year after study agent administration, long-term follow-up will be conducted annually for an additional 4 years after the Month 12 visit. At each of these visits, testing will include clinical evaluation, visual acuity and ophthalmic examinations. In accordance with regulatory guidance for gene therapy clinical trials, information will also be obtained about any cancer, neurological, autoimmune or hematological disorder that developed or worsened since the last visit in the form of a long-term follow-up questionnaire. The questionnaire is provided in Appendix B.

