### 7.3.6 Follow-up of Adverse Events

All SAEs and DLTs must be followed and treated as appropriate until resolution. An SAE or DLT is considered resolved when the subject returns to their baseline condition, or when the event has stabilized, as in the case of an event with sequelae, in which case the event will be noted as "resolved with sequelae".

If an SAE or DLT is still ongoing at the visit 12 months after study drug administration, follow-up of the event will be done at each follow-up visit until the end of the study.

If an SAE or DLT is still ongoing when the subject is lost to follow-up, the study site staff needs to complete the following steps to ensure the proper follow up the SAE or DLT:

- Complete and document two separate attempts to contact the subject and/or their emergency contact by telephone at an appropriate clinically indicated interval for followup of the event;
- If attempts to contact the subject are unsuccessful, send a certified letter to the subject's last known address requesting that the subject contact the study site.

Non-serious AEs that are assessed as "related" to the study agent will be followed and treated as appropriate until the end of the study, including evaluation at long-term follow-up visits if the event is ongoing at the visit 12 months after the study drug administration.

Non-serious AEs that are evaluated as "not related" to the study agent, and that are ongoing at the visit 12 months after the study drug administration, will be characterized as "ongoing" at that visit, and further follow up will not be required.

The investigator is responsible for ensuring that follow-up includes any supplemental investigations that may be indicated to elucidate as completely as practical the nature and/or causality of the AE or SAE. This may include additional laboratory tests or investigations, histopathological examinations, or consultation with other health care professionals.

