# 17 SUPPLEMENTS AND APPENDICES

The following appendices will be provided with this protocol:

- Time and Events Schedule
- Long-term Follow-up Questionnaire
- Summary of Protocol Changes
- Site-specific Signature Page
- Sponsor Signature Page

The following documents will also accompany this protocol:

- Sample Informed Consent Document
- Sample Child Assent Document
- Clinical Investigator's Brochure
- Study Manual of Procedures
- Manual of Procedures for Uploading Data to the Reading Center
- Pharmacy Manual
- Conflict of Interest Statement
- Common Terminology Criteria for Adverse Events v4.0
- Study Site and Sponsor Contact List

Time relative to study				D	ay				Mo	onth			Year	
agent administration	Screen a	BL⁵	0	1	7	14	1	2	3	6	9	12	2-5°	ET d
Visit Number	1	2	3	4	5	6	7	8	9	10	11	12	13-16	
Informed consent/assent	✓													
Inclusion/exclusion criteria	✓	✓												
Initial medical history	✓													
Blood for DNA testing e	✓													
Physical exam f	✓													
Safety labs f,g	✓				✓	✓								√*
Coagulation (PT and PTT) f	✓					1			l		1	1		
Blood for AAV antibodies	✓	1				İ	✓		✓	✓	İ	✓		✓
Blood for RS1 antibodies		✓					✓		✓			✓		✓
Blood for PBMC		✓					✓	✓	✓					√*
Blood for vector DNA		✓		✓	✓	✓								√*
Prophylaxis for inflammation		✓												
Study Agent Administration			✓											
Clinical Evaluation h		✓	✓	✓	✓	✓	✓	✓	✓	✓	✓	✓	✓	✓
Adverse Event Review		✓	✓	✓	✓	✓	✓	✓	✓	✓	✓	✓	✓	✓
Ophthalmic Examinations i	✓	✓	✓	✓	✓	✓	✓	✓	✓	✓	✓	✓	✓	$\checkmark$
Visual Acuity	✓	×2		✓	✓	✓	✓	✓	✓	✓	✓	✓	✓	✓
Octopus visual fields	✓	×2					✓	✓	✓	✓	✓	✓		$\checkmark$
Microperimetry	✓	×2					✓	✓	✓	✓	✓	✓		✓
Reading speed	✓	×2							✓	✓	✓	✓		✓
Contrast Sensitivity	✓	×2							✓	✓	✓	✓		✓
Electroretinography j	✓	✓							✓	✓		✓		$\checkmark$
Optical Coherence Tomography	~	×2					~	~	~	~	~	~		~
Fundus Photography		✓										✓		$\checkmark$
Quality of life questionnaire	✓	✓				İ			✓	✓	✓	✓		✓
Long-term follow-up questionnaire													~	

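### Protocol Section 4.3 and Appendix A disagree on who is offered an early termination visit, so delayed-event information since the last annual visit may be missed for participants who leave between Month 12 and Year 5

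*Protocol*

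**What the plan says.** Protocol Section 4.3 sets no time limit: "All subjects who prematurely discontinue from the study after administration of the study agent will be encouraged to complete an early termination (ET) visit". Footnote d of Appendix A does set one: "An early termination (ET) visit will be sought for any subject who withdraws from the study before the Year 1 visit". Footnote d to the schedule in SAP Section 4.2 carries the same limit.

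Protocol Section 6.15 describes the long-term phase: "long-term follow-up will be conducted annually for an additional 4 years after the Month 12 visit". At those visits "information will also be obtained about any cancer, neurological, autoimmune or hematological disorder that developed or worsened since the last visit", by means of a questionnaire. In the Appendix A table the questionnaire row is marked only in the Year 2-5 column, and its ET cell is blank. The row "Adverse Event Review" is marked at ET, as is Clinical Evaluation, which a footnote defines: "Clinical evaluation consists of an interim medical history, including use of carbonic anhydrase inhibitors and other medications, review of AEs", together with a symptom-directed examination.

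Section 7.3.6 prescribes two contact attempts and then a certified letter, on one condition: "If an SAE or DLT is still ongoing when the subject is lost to follow-up".

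SAP Section 16 reports the long-term information in a subject listing (Listing 16.2.14).

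**The concern.** Years 2-5 exist partly to monitor for delayed adverse events after a gene therapy, and safety is the primary objective. A participant who withdraws in, say, month 22 is asked for an exit visit under one rule and not under the other. If the site applies footnote d, nothing is collected at exit, and any new disorder arising since the Month 12 visit is recorded only if it happened to be reported in between. The contact steps in Section 7.3.6 would not help with a new and unreported disorder, because they apply only to an SAE or DLT already known and ongoing.

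Illness can itself be a reason for leaving, so the unobserved interval need not be a random sample of follow-up time. With about 27 participants, a single missed malignancy or autoimmune disorder would visibly change the delayed-event listing.

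**Working it through.** This is mainly a comparison of text. The arithmetic only sizes the gap.

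**Step 1. What each rule gives, by time of exit.**

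| Exit | Under Appendix A / SAP 4.2 footnote d | Under Protocol 4.3 |
|---|---|---|
| Before the Year 1 visit | ET visit sought; interim history and AE review included | ET visit encouraged; same content |
| Month 12 to Year 5 | No ET visit | ET visit encouraged; interim history and AE review included; questionnaire not marked |

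The rules conflict only in the second row.

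**Step 2. Does the ET column suit a late leaver?** After Month 12 the asterisked items (safety labs, PBMC, vector DNA) drop out by the footnote's own terms. The unasterisked items remain: AAV and RS1 antibodies, visual fields, microperimetry, reading speed, contrast sensitivity, ERG, OCT, fundus photography and quality of life. None of these is marked for Years 2-5 in the protocol. The Year 2-5 column has five rows: clinical evaluation, AE review, ophthalmic examination, visual acuity and the long-term questionnaire. So under Section 4.3 a late leaver would face tests no longer part of long-term follow-up and would not receive the one instrument specific to it.

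**Step 3. Time at risk per leaver.** Visits are annual, so the gap between the last attended visit and exit runs from 0 to about 12 months. With exits evenly spread between visits the mean is 12 / 2 = 6 months, or 0.5 years. Questionnaires and AE reviews from visits already attended are kept. Time after exit is unobserved under either rule.

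**Step 4. Time at risk for the trial.**
- Inputs: about 27 participants (Protocol Section 3) and 4 long-term years (Section 6.15). Planned long-term time = 27 × 4 = 108 person-years.
- The documents give no dropout rate. The proportion d leaving between Month 12 and Year 5 is an assumption, taken from 5% to 30%.
- Mean unascertained time = 27 × d × 0.5; maximum = 27 × d × 1.

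| d | Leavers, 27 × d | Mean person-years | Share of 108 | Maximum person-years |
|---|---|---|---|---|
| 5% | 1.35 | 0.675 | 0.6% | 1.35 |
| 10% | 2.7 | 1.35 | 1.3% | 2.7 |
| 20% | 5.4 | 2.7 | 2.5% | 5.4 |
| 30% | 8.1 | 4.05 | 3.8% | 8.1 |

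An assumed 5% per year falls inside this range: 27 × (1 − 0.95^4) = 5.0 leavers, and 5.0 × 0.5 = 2.5 person-years, about 2.3% of 108.

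**Step 5. Effect on stated figures.** None. The plan's only precision figures concern dose-limiting toxicity (Protocol Section 10.5) and do not depend on this rule. They reproduce with the exact two-sided 95% upper limit for zero events, 1 − 0.025^(1/n): 33.63% for n = 9 and 12.77% for n = 27.

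**The case against.** The strongest reply is that little is actually at risk, and most of it stands.

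- A reader might infer that delayed-event information is lost outright for everyone who leaves in Years 1-5. That requires footnote d to override Section 4.3, and nothing in the documents gives Appendix A precedence. Sites also use a Study Manual of Procedures, which is not among the documents. Even under footnote d, only the interval since the last attended visit is exposed.
- A reader might call this a gap over four of the five follow-up years. That counts calendar time in which an exit would have no ET visit. The information exposed is the roughly 0.6% to 4% of planned long-term time shown in the working.
- A reader might extend the point to someone leaving at month 10. The documents do not support this. The questionnaire is not given at any visit up to Month 12, and the ET visit includes interim history and AE review. Such a participant is questioned as he would be at Month 12. Within footnote d's own limit, leaving the questionnaire off ET is consistent.
- An ET visit held under Section 4.3 would still allow a new disorder to be recorded as an AE. Only the structured questions would be absent.
- The protocol's primary safety parameter (Section 7.1.1) covers the 12 months after dosing, and the SAP plans only a listing for the long-term information.
- Both rules are requests, so aligning them does not guarantee the data.

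What does not fall away is that two current passages give different instructions for the same participant, and that the ET column does not fit a late exit under either.

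**Conclusion.** The inconsistency is certain: Section 4.3 on one side, footnote d in both documents on the other. Its consequence is conditional and small. If footnote d is followed, delayed-event information since the last attended annual visit may be missed for participants leaving between Month 12 and Year 5. That is up to about 12 months each, and about 0.7 to 4.1 of 108 person-years in all on average. The size rests on three assumptions: about 27 dosed participants, 5% to 30% leaving in that period, and exits evenly spread between annual visits.

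The 12-month primary safety analysis is unaffected, and participants leaving before Month 12 are already covered by AE review at ET. The SAP's treatment-emergent AE tables state no 12-month limit, so a missed late event would be absent from those as well as from the long-term listing. Severity: minor.

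**What to change.** 1. In footnote d of Protocol Appendix A and of the SAP Section 4.2 schedule, replace the Year 1 limit with withdrawal at any time after study agent administration, to match Section 4.3.
2. In the same footnote, state that an ET visit after Month 12 consists of the protocol's existing Year 2-5 set (clinical evaluation, AE review, ophthalmic examination, visual acuity, long-term questionnaire) and not the full ET column. Without this, the first change would bring back for late leavers the efficacy tests that Version 8.0 took out of long-term visits.
3. Include the ET responses in Listing 16.2.14. The SAP is written for protocol Version 6.0: its schedule has no questionnaire row and still marks efficacy tests in Years 2-5, so it should point to the current protocol for the long-term set.
4. Optional: allow the questionnaire by telephone when the visit is declined.

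The cost is a footnote edit in two documents, a conditional mark for the questionnaire in the ET column, a small change to the listing, and one short visit or call per late withdrawal. No new test is added.

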# Appendix B. Long-term Follow-up Questionnaire

LO	NG-TERM FOLLO	OW-UP QUE	STIONNAIF	RE		Date:						
	olied Genetic	Protocol Number		Subj	Subject ID (three digit site, four digit number)							
	echnologies Corporation	AGTC-RS1	AGTC-RS1-001		<del>-</del>							
Ad	verse Events											
1.	1. Since your last evaluation for this study, have you had any unexpected illness or admission to a hospital?						sion to a					
		□ No □ Yes										
	lf yes, indicate th Adverse Event R		such events	s below, ar	nd describe e	each event c	on a Long-T	erm				
	□ 1	□ 2	□ 3	□ 4	D 5	D 6	□	*				
								events, write the vents on this line.				

#### Malignancies

2.	Since your last evaluation for this study, I been told that you have cancer)?	have you developed any new malignant tumor (have you
	□ No	□ Yes

#### **Neurological Disorders**

Since your last evaluation for this study, have you developed any new disease of your nerves or nervous system, or had any worsening of an existing disease of your nerves or nervous system?
 No
 Yes

#### **Rheumatologic or Other Autoimmune Disorders**

Since your last evaluation for this study, have you developed any new rheumatologic or other autoimmune disorder, or had any worsening of an existing rheumatologic or other autoimmune disorder? (Rheumatologic disorders are those that affect joints, and autoimmune disorders are those in which your immune system attacks parts of your own body.)
 No

#### Blood Disorders

5. Since your last evaluation for this study, have you developed any new blood disorder, or had any worsening of an existing blood disorder?
No
Yes

# Appendix C. Summary of Protocol Changes

Date	Protocol Version	Summary of Changes
06 Mar 2015	1.0	Original protocol
15 Mar 2015	1.01	Added IND number Corrected temperature at which study agent is stored
25 Mar 2015	1.1	

Within groups 4 and 5, enrollment of the first 3 pediatric participants in each group will be staggered by at least 2 weeks to allow adequate time for review of safety information by the investigators and sponsor.

Additional information about carbonic anhydrase inhibitor use added in sections 2.3.1 and 6.7.

06 May 2015	1.2	Modified injection volumes based on vector concentration of $4.3 \times 10^{12}$ vg/mL.
19 May 2015	2.0	Removed investigator signature pages and provided a site- specific signature page as an appendix. Removed section 1 and added a Sponsor and Study Site Contact List to section 17.
20 Oct 2015	3.0	Added steroid treatment for inflammation prophylaxis as recommended by the DSMC. Modified the study design to combine Groups 4 and 5 into a single group (a new Group 4), with no subject receiving a carbonic anhydrase inhibitor during the 6 months after study agent administration. Changed the point of contact for questions on SAEs from [name] to [name]. Modified the DLT definition to make the language more clear, and to leave the decision of the DLT assessment to investigator discretion. Modified the AE reporting and follow up responsibilities to make the language more clear. Corrected typographical and grammatical errors.

Date	Protocol Version	Summary of Changes
19 Apr 2016	4.0	Added risks for anterior chamber tap in Section 1.3.1.
		Clarified VA criteria for Groups 1A-4 by making the ETDRS letter score as primary enrollment criterion and revised ETDRS letter scores for each Group to include all ETDRS letter scores applicable to that Snellen equivalent calculated using ETDRS charts or EVA in Section 4.1.
		Based on discussions with investigators, revised intravitreal injection procedure language in Section 4.5 to indicate a single 0.14 mL injection is preferred.
		Updated static visual field analysis plan in Section 10.7.3.
17 June 2016	5.0	Revised estimated study enrollment duration pages 8 and 24. Corrected footnotes in study design table pages 9, 23 and 45.
		Added topical carbonic anhydrase inhibitor as an allowed medication to treat elevated IOP in section 5.7.
		Fixed minor typographical and formatting errors.
14 July 2017	6.0	Revised estimated study enrollment duration in the Protocol Summary and Section 3.
		Revised estimated number of participants in the Protocol Summary and Sections 3, 4, and 10.2.
		Modified the study design to include Group 2A throughout the protocol. Participants in this group will be 6-17 years old and receive the study agent at the middle dose.
		Added clarifications for the MTD throughout the protocol.
		Updated section 1.3.1 to further clarify risks related to the use of steroids.
		Added risks associated with anesthesia to section 1.3.1.
		Revised Sections 4.1 and 10.3 to include the new Group 2A and to clarify the washout period for CAIs.
		Updated Exclusion Criteria # 3 (section 4.3).
		Added clarification to Section 7.2.1.5 regarding SAE definition.
		Fixed minor typographical and formatting errors.

Date	Protocol Version	Summary of Changes
12 January 2018	7.0	Added risks associated with the study in Section 1.3.1. Added "Ocular Fluids" Section 6.5. Clarification added to the Storage of Samples for Future Research in Section 13.7.
21 October 2019	8.0	Removal of efficacy testing at LTFU visits: 12 month analysis revealed that AGTC-301 is generally safe and well-tolerated, but has no evidence of a treatment effect. Addition of LTFU questionnaire in Appendix B Updated publication policy

# SITE-SPECIFIC APPENDIX 1

15.9 16. 17. 18. 19. 20. 21. 22. 23.	5.8.2 Functional Vision Questionnaire for Children and Young People (FVQ_CYP) Fundus Photography Long-term Follow-Up (LTFU) Interim Analysis Data and Safety Monitoring Committee Changes from Protocol-Stated Analyses References Revision History Tables Listings					

List of Abbreviations

AAV	Adeno-Associated Virus
AE	Adverse Event
AGTC	Applied Genetic Technologies Corporation
ANOVA	Analysis of Variance
BCEA	Bivariate Contour Ellipse Area
BCVA	Best-Corrected Visual Acuity
CAI	Carbonic Anhydrase Inhibitor(s)
CRF	Case Report Form
CTCAE	Common Terminology Criteria for Adverse Events
DSMC	Data and Safety Monitoring Committee
eCRF	Electronic Case Report Form
ERG	Electroretinography or Electroretinogram
ETDRS	Early Treatment of Diabetic Retinopathy Study
ffERG	Full-field Electroretinogram
FVQ_CYP	Functional Vision Questionnaire for Children and Young People
HOV	Hill of Vision
ICH	International Conference on Harmonisation
IOP	Intraocular Pressure
logMAR	Logarithm of the Minimum Angle of Resolution
LTFU	Long-term Follow-up
MedDRA	Medical Dictionary for Regulatory Activities
mfERG	Multifocal Electroretinogram
MNREAD	University of Minnesota trademark for low vision visual acuity charts
MTD	Maximum Tolerated Dose
OCT	Optical Coherence Tomography
PCR	Polymerase Chain Reaction
PDF	Portable Document Format
PT	Preferred Term
rAAV	Recombinant adeno-associated virus
rAAV2tYF-CB-hRS1	Recombinant adeno-associated virus vector expressing retinoschisin
RS1	Retinoschisin (protein or gene)
RTF	Rich Text Format
SAE	Serious Adverse Event
SAP	Statistical Analysis Plan
SD	Standard Deviation
SDC	Statistics and Data Corporation, Incorporated
SD-OCT	Spectral Domain - Optical Coherence Tomography
SKP	Semi-automated Kinetic Perimetry
SOC	System Organ Class
VA	Visual Acuity
VFQ-25	25-question Visual Function Questionnaire

08 August 2017

XLRS	X-linked Retinoschisis
------	------------------------

1. Introduction

The purpose of this statistical analysis plan (SAP) is to describe the planned analyses and reporting for protocol AGTC-RS1-001, Version 6.0 dated 18 July 2017.

This SAP is being written with due consideration of the recommendations outlined in the most recent International Conference on Harmonization (ICH) E9 Guideline entitled Guidance for Industry: Statistical Principles for Clinical Trials and the most recent ICH E3 Guideline, entitled Guidance for Industry: Structure and Content of Clinical Study Reports.

This SAP describes the data that will be analyzed and the subject characteristics, efficacy, and safety assessments that will be evaluated. This SAP provides details of the specific statistical methods that will be used. The statistical analysis methods presented in this document will supersede the statistical analysis methods described in the clinical protocol. If additional analyses are required to supplement the planned analyses described in this SAP they may be completed and will be identified in the clinical study report.

2. Study Objectives

The primary objective is to evaluate the safety of recombinant adeno-associated virus vector expressing retinoschisin (rAAV2tYF-CB-hRS1) in patients with X-linked retinoschisis (XLRS). The secondary objective is to evaluate the efficacy of rAAV2tYF-CB-hRS1 in patients with XLRS.

3. Study Variables

